	8.4.1 Blinding	16
	8.4.2 Other measures taken to minimise/avoid bias	16
8.5	Intervention Procedures	16
8.7	End of Study/Trial Definition	17
10	Approvals	17
11	Safety & Adverse Events Reporting	17
11.1	Assessment of Safety	17
12	Compliance and withdrawal	17
12.1	Participant compliance	17
12.2	Withdrawal / dropout of participants	17
13	Data	17
13.1	Data to be collected	17
13.2	Data handling and record keeping	17
13.3	Access to the dataset	18
14	Statistical considerations	18
14.1	Sample size calculation	18

14.2	Statistical analysis	18
14.3	Interim analysis and data monitoring	18
14.3.1	Stopping/ discontinuation rules and breaking of randomisation code	18
15	Ethical considerations	19
16	Risk Management & Safeguarding	19
16.1	Risk Management	19
16.2	Safeguarding	19
17	Financing	19
18	Insurance	19
19	Publication and Dissemination	20
19.1	Publication	20
19.2	Informing participants	20
20	Disclosure of Interests	20

3 Summary/Synopsis

Full Title	Assessment Of the Volumetric Occlusal Adjustments Required For Michigan Splints Fabricated Using Various Digital Bite Registrations.
Short Title/Acronym	DIGI-OCCLUDE
Protocol Version number and Date	200524 – 31/5/2024
REMAS Number	43439
REC Name	Kings College London Research Ethics Committee
Study registration details (if applicable)	N/A
Chief Investigator	[name]
Sponsor name	King's College London
Funder(s)	The Hashemite University of Jordan
Population under investigation	Healthy Volunteers
Design & Methodology	Type of study/trial: controlled, Interventional
Study Duration	12 months
Primary objective	To evaluate volumetric changes on the biting surface of the occlusal splint following four different fully digital workflows. This will indicate the accuracy of the techniques in capturing the bite registration.
Secondary objective(s)	
Number of Participants	40
Endpoints	Using the digital facebow along with the digital record of occlusion (retruded articular position (RAP) versus intercuspal position (ICP)) will result in less modification at the fit appointment.
Main Inclusion Criteria	Able to provide an informed consent and having no more than one tooth missing per quadrant.
Main Exclusion Criteria	Participants who are Edentulous or wearing partial dentures
Statistical Methodology and Analysis	ANOVA statistical test will be used to compare means across the 4 groups. If the mean values between the comparison values between the groups are statistically significant or not.
Data to be collected & associated storage arrangements.	Baseline data, including intraoral scans, clinical photographs, and digital facebow, will be obtained for each participant. This data will serve as a reference for both digital and semi-digital occlusal assessments. The data will be processed under the terms of UK data protection law (including the UK General Data Protection Regulation (UK GDPR) and the Data Protection Act 2018).

4 Introduction

Temporomandibular disorder (TMD) is significant public health condition affecting the movement of the lower jaw and is mainly due to teeth grinding during sleep or sometimes by teeth clenching during the day. It can manifest as pain around the ear, clicking sounds when moving your jaw, wear of dental tissues, headaches, difficulty in mouth opening, and sometimes jaw locking. Those symptoms usually get worse when the patients are under stress. It is not usually serious and generally gets better on its own, however in many cases, it requires further consideration. Management of this disordering, soft diet, painkillers, physical joint exercises. Furthermore, for many cases, dentist may decide to fabricate an occlusal splint (Michigan splints) that fits in the upper teeth, to prevent further damage to the teeth and it may help with pain relief, as it positions the joint in a comfortable position.

Traditionally, these devices are fabricated by taking impressions in the clinic for both jaws and pouring these impressions in the lab, waxing up then fabricating the occlusal splints. Dental treatment can be a lengthy and expensive process for the dental technician, the dentist, and the patient. Therefore, it is important to understand the production accuracy, cost, and reproducibility of newly introduced digital methods. Following the design of the dental prosthesis, the prosthesis must be adjusted manually with use of a mechanical articulator increasing both cost and time. Thanks to the improved advancements in dental technology, dentists can use virtual reality in recording and analysing static and dynamic occlusion as well as jaw relation.

Review of literature

Occlusion: is defined as the static relationship between the incising or masticating surfaces of the maxillary or mandibular teeth or tooth analogues and it's considered a critical component for diagnosing and executing a prosthodontic treatment plan, using either conventional or digital methods.¹

Clinical treatment often requires modifications to the dental occlusion for restorative or prosthetic practice.^{2,3} even though most patients adapt to their new occlusion easily, some can develop discomfort and pain, mostly in the presence of an occlusal interference⁴; Irregular occlusal contacts can lead to congestion of the teeth and the appearance of various clinical symptoms, such as migration of the teeth, cracked enamel, darkening of the teeth, atrophy of periodontal tissue, gingival recession, defects in filling or crowns, osteoarthritis of implants, diseases of the TMJ, migraine, and orofacial pain.^{5,6,7} Therefore, occlusion analysis systems should meet minimal accuracy standards to detect, quantify, and locate occlusal contacts.

A common way to record the occlusal contacts is the articulating paper which is rapid, affordable and available in different thicknesses.^{8,9} Another way is the silicone occlusal registration, scanned with a light source and analysed by using an image software program, has reported to offer the highest reliability and validity for determining the occlusal contact area (OCA)^{10,11} and its claimed to be the ideal and standard method.¹² Recently introduced digital systems, including the T-Scan and digital casts, have also become available for occlusal assessment.¹³ And their application in oral rehabilitation represents a significant advancement in dentistry. This technology leverages digital tools to analyse and plan occlusal relationships, contributing to more precise and personalized oral rehabilitation outcome. The mechanical articulator is a physical instrument that facilitates reproduction of the relationship between the jaws and the skull base, as well as mandibular articulation, in relation to each of the three spatial planes. With improvements in technology, the articulator is shifting from a mechanical device to its digital alternative, the virtual articulator which involves software tools.¹⁴ A virtual articulator is a computer software tool that can reproduce the relationship between the jaws and simulating jaw movement. It has gradually gained research interest in dentistry over the past decade. In prosthodontics, the virtual articulator should be considered as an additional diagnostic and treatment planning tool to the mechanical articulator, especially in complex cases involving alterations to the vertical dimension of occlusion (OVD). To correctly simulate jaw movement, the jaw models must be digitalized and properly mounted on the virtual articulator.¹⁵

The main indication for the virtual articulator is to overcome the main issues with the mechanical articulator, such as creation of new occlusal contacts, material deformation, errors during orientation and positioning of dental casts, and difficulties simulating patient data in three dimensions. Those articulators may also be used as an educational tool to display treatment options to patients.¹⁶ Mounting casts on an articulator is necessary for the diagnosis of malocclusion and allows an assessment of occlusal alterations during the treatment planning phase. The essential elements common to all available virtual articulator are data acquisition and transfer of the arches to the virtual environment, and subsequent articulation of virtual models which includes (1) digital impression of the arches by the intraoral scanning ; (2) recording of static occlusion and excursive movements of the mandible; (3) transferring the position of the maxilla relative to the skull by the use of facebow ; and (4) mounting the virtual models on the articulator.

Facebows are essential and a key point in dental treatment, for a very important reasons, relating the maxillary arch to the condyles. The use of virtual facebows is a critical aspect of assembling digital models in a virtual articulator. During virtual articulator mounting, it is essential to orient the arches

with respect to a reference plane from the patient's head; using a virtual facebow is used. As the mechanical facebows, virtual facebows can be categorized using average values or by kinematics. Prior

toits use the clinician needs to identify a reference plane. Any such reference plane passes through three points: two at the posterior, and one at the anterior. The two posterior landmarks (arbitrary or anatomical) determine a terminal transverse hinge axis. Kinematic facebows involve the identification of the rotational hinge axis using cutaneous landmarks to pinpoint anatomical condylar projections and can therefore be more precise.¹⁷

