6.1 Study/Trial Design

This clinical trial will be conducted on 40 participants, each will receive an occlusal devices according to the grouping below. Group

Group	Group A	Group B	Group C	Group D
Criteria	Without digital facebow at ICP	With digital facebow at ICP	Without digital facebow at RAP	With digital facebow at RAP

The clinical and the lab steps:

This clinical trial will need 2 clinical visits:

VISIT ONE:

1-Participant information and informed consent.

Before participation, all participants will be provided with a detailed informed consent form outlining the purpose of the study, the procedures involved, potential benefits, and risks. Participants will be given the opportunity to ask questions before providing written consent.

2-Dental photography including Frontal, Right buccal, Left buccal, Upper occlusal, Lower occlusal views.

3- Digital facebow using the **AxioSnapMount Facebow-Germany**. It typically consists of adjustable earpieces and a bite fork, which are attached to the patient head, the bite fork is inserted into the patient's mouth, and the patient is guided to bite down into occlusion, Once the bite position is scanned, the AxioSnapMount facebow is removed from the patient's head. And the data are transferred as STL file into the program.

4- Digital impression of upper and lower teeth using **Intraoral Scanner (IOS) (Primescan, Sirona)**. Clinical conditions at the time of scanning the patient will be IOS calibrated before each scan according to the manufacture's recommendations, operatory temperature is at room temperature, Optragate will be used to separate the cheeks and saliva suction at the beginning of each arch scan and operatory light will be turned off. The IOS start on the occlusal of the maxillary right second molar, continues along the occlusal surfaces of the adjacent teeth to the left maxillary second molar, continues toward the buccal side of the same left maxillary second molar to the buccal side of the right second molar, and ends with a scan of the lingual side of the same molar to the left maxillary second molar, continues toward the buccal side of the same left maxillary second molar to the buccal side of the right second molar, and ends with a scan of the lingual side of the same molar to the left maxillary second molar.

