5- Bite registration: A Lucia gauge will be used to separate the maxillary and mandibular teeth for 5 minutes to deprogram the muscles of mastication. The participant will be guided to occlude on the lucia jig to protrude and perform lateral excursions of the mandible without posterior tooth contacts. The position will be recorded with a polyvinylsiloxane occlusal recording material (O-Bite; DMG). Then the teeth will be dried with an air syringe to minimize the influence of saliva on scanning accuracy. the intraoral scanner will scan the maxillary and mandibular dentition and the maxillomandibular bite relationship in the **retruded articular position (RAP)**. While obtaining the occlusal relationship, the occlusal record will be located on one side to scan the teeth on the other side.

6- Another bite record will be taken where teeth meet normal together, as soon as **Intercuspal position (ICP) and scanned** by the IOS.

LAB PROCEDURE:

1- All groups will be mounted digitally on average value virtual articulator.

Group A. Export the scans for the **CAD design** in Standard Tessellation Language (STL) files and processed for virtual mounting the models on virtual articulator with **average values**. The average digital articulator will use average values (Bennett angle=10 degrees; immediate side shift=0.5 mm; condylar angle=30 degrees; angle incisal table=30 degrees) as its parameters with the use the ICP record.

Group B. The scanned **facebow fork** will be imported and matched to the software for the maxillary mount. And the fabrication of the occlusal splint with the ICP record.

Group C. The models will be mounted using the RAP record only.

Group D. The models will be mounted using the digital facebow and the RAP record.

- 2- **Design** the occlusal splint based on the patient's specific dental anatomy, considering factors like the bite, occlusion, and any specific requirements for the splint.
- 3- **Printing:** load the digital file and a 3D printer Sprintray **will be** used to print all the digital occlusal devices based on the digital design. These digital devices are to be printed from.
- 4- **Polishing:** Apply a biocompatible polish (Sof-Lex™ Finishing and Polishing System by 3M).
- 5- Scan the splint by using lab scanner (3 shape E3) the splint with optical spray to overcome the translucency issue while scanning (Telescan CAD Spray White).

VISIT 2:

Patient fitting

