-Try the digital occlusal splint on the patient to ensure a proper fit and make any necessary occlusal adjustment.

-Scan: after the required occlusal adjustments are done, the splints are scanned again.

The next step:

The STL files of both scans of the occlusal device will be imported into a reverse engineering software program (**Geomagic Wrap 2021; 3D Systems**), and the root mean square (RMS) values will be used to represent the volume of occlusal adjustment and will be obtained by the “best fit alignment” and “3D compare” function. the occlusal adjustment positions will be standardized according to the 3D deviation scale diagram in the software program.

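### Occlusal adjustment measured on the splint cannot show how accurately the bite was captured when ICP groups are compared with RAP groups; the synopsis should claim only the amount of adjustment each workflow needs

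*Combined protocol and SAP*

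**What the plan says.** The primary objective in the synopsis (section 3) is to evaluate volumetric change on the biting surface of splints from four digital workflows. It then interprets that change: "This will indicate the accuracy of the techniques in capturing the bite registration". The synopsis endpoint brings jaw position into the comparison: "retruded articular position (RAP) versus intercuspal position (ICP)) will result in less modification at the fit appointment".

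Section 6.1 sets out a two-by-two grouping. Groups A and B use the ICP record and groups C and D the RAP record, each without and with the digital facebow (group A, for example, is "Without digital facebow at ICP"). The two records are obtained differently:

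- RAP: "A Lucia gauge will be used to separate the maxillary and mandibular teeth for 5 minutes to deprogram the muscles of mastication". Then: "The position will be recorded with a polyvinylsiloxane occlusal recording material (O-Bite; DMG", followed by an intraoral scan.
- ICP: "Another bite record will be taken where teeth meet normal together", also scanned.

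At visit 2 the instruction is: "Try the digital occlusal splint on the patient to ensure a proper fit and make any necessary occlusal adjustment". The splint is scanned again, and the RMS deviation between its two scans after alignment stands for the volume adjusted.

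The null hypothesis (5.1) and the primary objective in the body (5.2) concern volumetric change only and make no statement about accuracy. The synopsis gives one outcome analysis, an ANOVA of the four group means. Section 13.2 covers recruitment and retention only.

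**The concern.** The amount ground off a splint measures the error of a bite record only if two conditions hold: the record aimed at the position to which the splint is later adjusted, and nothing else differs between the groups. The plan secures neither for ICP versus RAP. A faithfully captured ICP record could need substantial adjustment because the operator adjusts to some other position, and the outcome would look the same as poor capture.

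What is at stake is the stated conclusion of the primary objective. If A and B need more adjustment than C and D, the synopsis sentence invites a report that one bite-capture technique is less accurate. The data would show only that one complete workflow needed more chairside change.

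**Working it through.** **Step 1. What changes between A/B and C/D (section 6.1).**

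| Feature | A and B (ICP) | C and D (RAP) |
|---|---|---|
| Jaw position recorded | Intercuspal | Retruded |
| Teeth at recording | Together | Separated on a jig, after 5 minutes of deprogramming |
| Procedure | Bite record, scanned; no material named | Silicone record, scanned |
| Position adjusted to at visit 2 | Not stated | Not stated |
| Reference jaw relation in the outcome | None | None |

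The first three rows change together, so no contrast among the four groups separates them.

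**Step 2. What the outcome can see.** It compares a splint with itself before and after adjustment. No repeat record or reference position is compared with the original record. Between record and fitting lie virtual mounting, design, printing and polishing, and any of these can also create a need for adjustment.

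**Step 3. The two readings of visit 2.**

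- *All splints adjusted to one common position.* At least one record type aimed elsewhere, so its adjustment includes that offset as well as record error.
- *Each splint adjusted to its own recorded position.* The offset disappears, but the groups then have different targets and recording procedures, and the later workflow steps still contribute.

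Neither reading isolates capture accuracy.

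**Step 4. The plan's own figure.** 4 groups × 10 = 40 participants, as stated in section 13.1. The plan gives no effect size, SD or power, and no alpha for this trial, so nothing further can be reproduced.

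**Step 5. Hypothetical illustrations.** None of the inputs below comes from the documents except 10 per group. Both illustrations place the offset on the ICP groups by assumption.

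(a) Suppose both records have the same error e = 0.10 mm, ICP splints carry an independent offset s, and RMS = √(e² + s²).

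| s (mm) | Calculation | ICP reading (mm) | Ratio to 0.10 |
|---|---|---|---|
| 0.05 | √(0.0100 + 0.0025) | 0.112 | 1.12 |
| 0.10 | √(0.0100 + 0.0100) | 0.141 | 1.41 |
| 0.20 | √(0.0100 + 0.0400) | 0.224 | 2.24 |
| 0.30 | √(0.0100 + 0.0900) | 0.316 | 3.16 |

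(b) Suppose capture accuracy is equal and the ICP group means are higher by d SD from position alone, with alpha 0.05. The noncentrality is λ = 10 × 4 × (d/2)² = 10d². Degrees of freedom are 1 and 36 for the ICP-versus-RAP main effect and 3 and 36 for the four-group ANOVA.

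| d | λ | P(main effect significant) | P(ANOVA significant) |
|---|---|---|---|
| 0.25 | 0.625 | 0.12 | 0.09 |
| 0.5 | 2.5 | 0.34 | 0.21 |
| 0.8 | 6.4 | 0.69 | 0.50 |
| 1.0 | 10 | 0.87 | 0.71 |
| 1.5 | 22.5 | 0.996 | 0.98 |

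A significant result could therefore arise with no difference in capture accuracy. How likely that is here cannot be known from the documents.

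**Step 6. The contrasts within one record type.** B versus A and D versus C hold record type fixed, so this confounding does not touch them. Each compares 10 participants with 10 others, so its standard error is √(1/10 + 1/10) = 0.447 SD.

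**The case against.** The strongest reply is that this is one explanatory sentence in a synopsis. The title, the null hypothesis, objective 5.2 and the synopsis endpoint all concern adjustment or modification needed. The sentence before the quoted one already speaks of workflows, and no group, measurement or test depends on the accuracy claim. ICP versus RAP is also the factor under study, so the fact that it changes several things at once is no flaw in a comparison of adjustment needed. All of this stands, and it limits the point to the interpretation. It does not rescue the sentence, which is the declared meaning of the primary objective and goes beyond 5.1 and 5.2.

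Three further objections also stand in part:

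- A reader might infer that finished ICP and RAP splints differ in vertical opening. Section 6.1 shows tooth separation when the RAP record is taken. It gives no splint thickness or design opening for any group, so a difference between finished splints is an inference.
- A reader might infer that splints are adjusted to a position other than the one recorded. Section 6.1 does not say. The gap is that the position is unstated, not that it is shown to be wrong.
- A reader might take the factors in step 5(a) as the expected bias. They follow entirely from assumed inputs, and nothing in the documents supports that formula as the link between record error and the RMS of two aligned splint scans.

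**Conclusion.** The point holds as a limit on what may be concluded. Because jaw position, tooth separation and recording procedure change together, the outcome has no reference jaw relation and the adjustment position is unstated, an ICP-versus-RAP difference cannot be attributed to accuracy of bite capture. This rests on the text of section 6.1 and needs no numerical assumption. The size of any distortion is unknown.

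Two stronger conclusions might be drawn, and the documents support neither. One is that the ICP-versus-RAP comparison is invalid; it remains a proper description of how much adjustment each workflow needs. The other is that the facebow contrasts are a clean substitute. They avoid this confounding but concern the maxillary mounting, not the bite record. They also compare different participants with 10 per group, and allocation is unclear: section 9.1 has volunteers randomised after consent, while section 10.1 says there is no randomisation.

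The change should be made: it alters what the primary objective may claim, while the data and procedures stay usable as planned.

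**What to change.** 1. In the synopsis, replace the accuracy sentence with: *This will indicate the amount of chairside occlusal adjustment each complete workflow requires.* This agrees with 5.1 and 5.2.
2. Beside the ANOVA in the synopsis, and in 5.2, state that ICP-versus-RAP differences are attributed to the workflow as a whole and not to record accuracy.
3. Base any statement about facebow mounting on B versus A and D versus C, named in advance as planned comparisons. Report them as between-participant comparisons with 10 per group.
4. Reconcile sections 9.1 and 10.1 on randomisation, since the reading of those contrasts depends on it.

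It would also help readers if section 6.1 stated the position and end-point used for adjustment at visit 2. Which they should be is a clinical matter and is not proposed here.

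The cost is a narrower claim and two added contrasts, which have limited precision at this sample size. Items 1 to 3 leave the groups, scans and visits unchanged.
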